Visit 1: BASELINE visit at the time of recruitment (flexible time point but not within the 4 week period after vaccination)

Visit 2: PRE-VACCINATION visit (omitted if less than 12 weeks after visit 1)

Visit 3: PEAK IMMUNE RESPONSE post vaccination (4-10 weeks after vaccine dose)

Visit 4: LONGEVITY of immune response post vaccination (24-36 weeks post vaccine dose)

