9.1 Anti-spike antibody testing

Antibodies will be tested using the Roche spike IgG quantitative assay (Birmingham). The assay detects anti-spike antibodies against the original Wuhan strain and so is suitable for detecting vaccine responses in a quantitative way. It will also detect antibodies following infection and cannot distinguish between these. It will be the primary platform to be used for all participants as it is already in widespread use by PHE and in the NHS. The Roche assay has been validated in Birmingham for DBS and shows excellent correlation and concordance with serum in providing a quantitative result. This remote sampling has been widely used for COVAD and other COVID-19 studies (PANORAMIC, COVIDENCE). To ensure applicability, the Roche assay performance will be compared with other platforms in use in the NHS using World Health Organisation (WHO) reference serum. This assay can be used to assess blood and mucosal samples.

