- · Occupation, nature of work and type of personal protective equipment used during that work
- Medical conditions (self- reported)
- latrogenic immunosuppression (or within 6 months of iatrogenic immunosuppression including chemotherapy)
- · Vaccination history including COVID-19, influenza, and any test vaccines given
- · Known prior infection

Behavioural variables

If the participant self-isolated as a result of an illness in a household contact, we will collect data on the nature of that illness (when was illness, symptoms, severity, duration) and how many other household contacts were unwell.

Serological response

Time points for serological measurements: Assessment at 4 timepoints (Visit 1: baseline visit, Visit 2: before next vaccine dose, visit 3: 4 weeks post vaccine dose and Visit 4: 24-36 weeks post vaccine).

ii) 'Low' antibody range: Antibody values which lie within the lower 10th percentile of range of IgG antibody concentrations in HC following vaccine dose.

General analysis principles

- Summary statistics will include either mean, standard deviation, and/or median, interquartile range for continuous variables as appropriate to the distribution and n (%) for frequencies.
- The amount of missing data will be reported. Analysis will be of complete data and missing data will not be imputed.
- 5% two-sided level of statistical significance, with corresponding 95% confidence intervals presented where applicable.
- No adjustments for multiplicity are planned.

Planned analyses and reporting:

Primary Outcome

To assess the additive value of serological responses to CV status in predicting infection

The binary infection outcome will be captured by recording the timing and incidence rates of all infections from ≥14 days post vaccination given between Visit 2 until Visit 4 will be reported in the total combined CV groups, and by individual CV groups. We will describe the number and proportion of infections for each level of antibody response post-V3 (no, low, normal)

The primary analysis will be undertaken using a logistic regression model with infection as the outcome and antibody response post-V3 as a binary variable as the exposure. We will present odds ratios with 95% confidence intervals for the unadjusted model, as well as for a model adjusted for the baseline and behavioural variables as well as any COVID-19 therapy received in the community, preadmission and in hospital (where data available).

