To assess serological responses, antibody boosting, antibody waning and correlation with infection

The above analyses focus primarily on Visit 3 (4 weeks post vaccine booster). Similar analysis will be performed from antibody status at time point Visit 1, with adjustment required for time post-vaccine to Visit 1, and also vaccine type pre-Visit 1 (Wuhan or bivalent vaccine). Infection outcomes will be described up until Visit 2. Assessment of waning (rate of antibody concentration decline) will also be described between Visit 1 and Visit 2. Assessing differences between HC versus CV group, but also individual groups. Similar waning analysis will be reported between Visit 3 and Visit 4.

Descriptive changes in antibody levels between Visit 3 and Visit 4 by CV groups will also be reported.

Sponsor: University of Birmingham

Antibody binding to VOC

This analysis will be focused on samples derived from Visit 1 and at subsequent follow up points, assuming this will capture most diversity in VOC during the study duration. Antibody binding to SARS-CoV-2 WT will be compared against binding to the dominant VOCs in participants with detectable antibodies and reported as fold-change (e.g. VOC/WT) and absolute change.

Subgroup analyses

We will present the number and proportion of patients with adequate and inadequate antibody response in each disease subgroup. We will also present the number and proportion in each of these groups with COVID-19 infection and COVID-19 related hospitalisation. Provided there are sufficient numbers in each group, we will undertake exploratory analyses using the same approach as for the analysis of the primary outcome in the full cohort.

Exploratory Analyses

Evaluation of QCOVID4 risk score

i) Is the QCOVID4 score associated severe COVID-19 in our cohort? (low/med/high and quantitative analysis)

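### The primary analysis counts infections from day 14 after vaccination, but the antibody exposure is sampled at weeks 4-10, so early infections can alter the exposure and pull the odds ratio downwards

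*Protocol*

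**What the plan says.** Under Primary Outcome, Appendix 3 of the protocol defines the binary infection outcome by "recording the timing and incidence rates of all infections from ≥14 days post vaccination given between Visit 2 until Visit 4". The primary logistic model takes "antibody response post-V3 as a binary variable as the exposure". That V3 means Visit 3 is clear from a later sentence in the same appendix: "The above analyses focus primarily on Visit 3 (4 weeks post vaccine booster").

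The visit schedule in section 6.1 gives "Visit 3: PEAK IMMUNE RESPONSE post vaccination (4-10 weeks after vaccine dose") and "Visit 4: LONGEVITY of immune response post vaccination (24-36 weeks post vaccine dose"). Section 6.5.1 and Appendix 2 repeat the 4-10 week window for Visit 3, whereas Appendix 3 describes the visit as 4 weeks or 28 days after vaccination.

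On the primary assay, section 9.1 states: "It will also detect antibodies following infection and cannot distinguish between these". Nucleocapsid testing, which could identify infection, appears in section 9.2 only as a possible exploratory assay.

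Nothing in the protocol restricts the primary outcome to infections after the Visit 3 sample, removes people infected between vaccination and that sample, or adjusts for such infections. Known prior infection is listed only as a baseline characteristic. The competing-risk sensitivity analysis states no time origin. For antibody decline, the appendix adds: "Similar waning analysis will be reported between Visit 3 and Visit 4".

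**The concern.** Outcome counting starts 2 to 8 weeks before the exposure is measured. Someone with a poor vaccine response who is infected at week 3 and sampled at week 8 may show a high anti-spike level because of the infection, and is then recorded as a normal responder who became infected. The outcome has changed the exposure. The misclassification runs one way: infected people leave the low group and join the normal group.

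The primary objective is the predictive value of serology. An infection that occurred before the sample cannot be predicted by it, whatever the size of the bias. The prediction model with its C statistic and the severe-outcome analysis follow the primary approach and inherit the problem. The waning analyses have a related one: an infection between two samples masks the decline they are meant to measure.

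**Working it through.** **Inputs from the protocol.** Outcome window: week 2 to Visit 4 (weeks 24-36). Exposure: Visit 3 (weeks 4-10). Planned split: 750 low/no and 2250 normal responders, 90% power, two-sided 5% (Appendix 3).

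**Assumptions not in the protocol.** Infection rates other than the 50% case; constant hazard; the share c of early-infected low responders lifted into the normal group; no lag between infection and antibody rise in the closed form.

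**1. The plan's own figure.** A two-proportion test with 750 and 2250 gives a detectable difference at 90% power of 6.8 points at a 50% rate, 6.4 at 30%, 5.7 at 20%, 4.4 at 10% and 3.4 at 5%. The statement that the difference is below 10%, and often below 5%, reproduces.

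**2. Share f of the window that precedes the sample.**
- Smallest: (4−2)/(36−2) = 2/34 = 6%
- All samples at week 4: 2/34 to 2/22 = 6% to 9%
- Mid-window (Visit 3 at week 7, Visit 4 at week 30): 5/28 = 18%
- Largest (week 10 and week 24): 8/22 = 36%

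**3. Effect on the odds ratio (low versus normal).** Moving a fraction f·c of infected low responders into the normal group gives

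observed OR = true OR × (1 − f·c) / (1 + [750·pL / (2250·pN)]·f·c).

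Take pN = 20% and pL = 27.3%, a true OR of 1.5. The bracket is 204.5/450 = 0.4545. Example for f = 5/28, c = 0.8: f·c = 0.143, and 1.5 × 0.857/1.065 = 1.21.

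| f | c = 0.25 | c = 0.5 | c = 0.8 |
|---|---|---|---|
| 6% | 1.47 | 1.44 | 1.40 |
| 9% | 1.45 | 1.40 | 1.35 |
| 18% | 1.40 | 1.31 | 1.21 |
| 36% | 1.31 | 1.13 | 0.94 |

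With a true OR of 1 the bracket is 1/3. At c = 0.5 the observed OR is 0.96, 0.88 and 0.77 for f = 6%, 18% and 36%.

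**4. When the estimate reaches the null.** Setting the observed OR to 1 at a 20% rate gives f·c = 0.15 for a true OR of 1.25, 0.26 for 1.5 and 0.39 for 2. Since f is at most 0.36 at constant hazard, a true OR of 2 does not reach the null even with c = 1.

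**5. At the design's own effect.** At a 20% rate the detectable 5.7 points is an OR of 1.38. With f = 6% the observed OR is 1.35 (c = 0.25) to 1.27 (c = 1), and power falls to between 86% and 66%.

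**6. Simulation check.** 3000 people, Visit 3 uniform on days 28-70, Visit 4 at day 210, antibody rise after 0 or 14 days, c from 0.25 to 1, 400 repetitions. With a true OR of 1.38 the planned analysis gives 1.01-1.31, and counting only infections after the Visit 3 sample gives 1.36-1.38. With a true OR of 1.00 the planned analysis gives 0.76-0.96 and the restricted count 1.00.

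**7. Cost of the restricted count.** At a 20% rate and f = 6%, 737 low responders at 24.4% are compared with 2221 normal responders at 18.9%: power 88%. At f = 36%, 673 at 17.2% against 2075 at 13.2%: power 72%. Across rates of 10-50%, power is about 88% at f = 6% and 68-73% at f = 36%.

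**The case against.** Appendix 3 repeatedly places Visit 3 at about four weeks. If sampling keeps to that, the overlap is only 6-9% and the result is mild attenuation. A lag between infection and antibody rise shrinks it further: with a 14-day lag and week-4 sampling, reclassification is close to nil. The lifted share c is not in the protocol, and section 2.0 describes these populations as poor vaccine responders, so a high c is not assured. All of this stands and limits the size. It does not remove the fault: 4-10 weeks is the window in the visit schedule, Appendix 6 makes it only an ideal for people recruited after their booster, and even week-4 sampling leaves two weeks of outcome before the test.

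The phrase post-V3 might be read as limiting the count to infections after Visit 3. It qualifies the antibody response, however, and the stated count begins at day 14.

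A reader might infer three stronger points, none of which the protocol supports:

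- **That the association will be reversed.** The 0.94 above needs the largest overlap for the whole cohort, 80% reclassification and a modest true effect.
- **That the claim of prediction is void.** With week-4 sampling, over 90% of the window follows the sample.
- **That unequal follow-up biases the primary odds ratio.** A hazard giving 20% at 28 weeks gives 1 − 0.8^(22/28) = 16.1% at 22 weeks and 1 − 0.8^(34/28) = 23.7% at 34, an OR of 1.62. That compares follow-up lengths, not antibody groups. With windows spread uniformly over 22-34 weeks independently of antibody status, the OR is 1.498 against 1.500 with a fixed window. Nothing in the protocol suggests that Visit 4 timing depends on antibody status.

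The competing-risk analysis cannot be called wrong outright, because no time origin is stated and a separate SAP may give one. As written, it offers no protection.

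**Conclusion.** The point holds. The outcome window opens before the exposure is measured, the assay lets an early infection raise the exposure, and the protocol contains no safeguard. The main effect is a downward bias in the odds ratio, which for a harmful effect of low antibody means attenuation. For a true OR of 1.5 and 25-80% reclassified, the observed value is about 1.35-1.47 with week-4 sampling and 1.21-1.40 at mid-window. A true null can appear as an OR below 1. Reversal is confined to late sampling, high reclassification and a true OR of about 1.5 or less.

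These sizes rest on constant hazard, assumed infection rates and an assumed reclassification share. If low responders rarely reach the normal range after infection, the bias is small; if infections peak soon after the booster, the overlap could exceed the range shown. The ordering problem does not depend on these assumptions. It matters because the study is sized to detect small to moderate effects on infection.

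**What to change.** - In the primary logistic model, the prediction model, the severe-outcome analysis and the competing-risk analysis, count only infections after the Visit 3 sample (a landmark at that date).
- Either exclude participants infected between vaccination and Visit 3, or carry that infection as a covariate. Choose one in advance and run the other as a sensitivity analysis.
- Report infections before Visit 3 descriptively.
- In the waning analyses, exclude or flag participants infected between the two samples.
- Leave the odds-ratio model and the Visit 4 endpoint as they are. Once its clock starts at the Visit 3 sample, the planned time-to-event analysis can handle unequal follow-up.

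No new data are needed if sample and infection dates are recorded as planned. The cost is fewer primary events, so power must be restated for the shorter window: about 88% if 6% of it is lost, and about 68-73% if 36% is lost. Sampling close to week 4 keeps that loss small.

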There will be a baseline visit which will establish an antibody result at the point of recruitment and establish their medical and COVID-19 infection and vaccination history. There will be 3 further visits that will measure the antibody level prior to booster vaccination, the antibody response at 4-10 weeks post vaccination and then a 4th visit at least 24 weeks after vaccination to examine the longevity of this booster response. Patients can be recruited at any point during their vaccine journey (pre or post vaccine). If patients are recruited after their booster vaccination, they will start at visit 1. Clarification of this route is shown in Appendix 6. Patients will receive their antibody test result.

Booster vaccinations are not being given as part of the study; it is the antibody response to any vaccines that are being given as part of the national vaccination policy that are being examined. If an individual chooses not to have a vaccine they will still be able to take part and we will still measure their antibody levels at equivalent timepoints to those being vaccinated.

Participants will contact the study team or their local clinic team if they test positive for COVID-19 infection, which will enable the study team or local clinical team to complete an online form relating to their illness and to send swabs back to the study to monitor for persistent viral infection.

For participants in the remote cohort (2600) their 4 visits will be all be undertaken remotely but with the option for in person or assisted consent if required. Their contact with the study will be either over the telephone or electronic. They will receive regular electronic updates on the study from the Central Study Team and will have the email and telephone for the Central Study Team if they would like or require individual contact. In addition to this, individuals may receive a telephone call to clarify any history provided by the participant remotely during visits 2-4 or if they suffer from COVID-19 infection. Patients will also be texted their result.

For participants in the in-person cohort (400) they will be enrolled either remotely or in-person and all 4 visits will be in-person to enable an extended sample collection. Contact about the study will then be similar to the remote cohort.

Sponsor: University of Birmingham

Participants will be monitored for COVID-19 infection until the study completes.

FIGURE 1. Visit schedule

3000 participants

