6.5.1 Timing and detail of visits

These visits are arranged around the assumption that there will be a booster campaign, but we acknowledge the study will have to be amended if this is not the case.

Visit 1: Baseline – This is a flexible timepoint depending on recruitment.

At the baseline visit (remote and in-person) patients will be contacted by a research nurse or member of the study team to populate the CRF. The research team member will complete the REDCap online CRF form through this telephone call, with the information detailed below, from the participant. The study team will also be able to confirm clinical details through hospital records, GP records and NHS digital records (e.g. hospital episode statistics and the National Immunisation Management Service) which the patient has consented to. This information will be inputted straight into the REDCap database by the research team. Where this is not possible, for contingency the data will be collated on paper and transcribed onto an electronic CRF on the REDCap secure web application.

The research nurse or clinical team will collect the following data from the hospital records, GP records, National Immunisation or Vaccination System or NHS digital.

Medical conditions / co-morbidities and regular/previous medication as detailed in CRF

 Vaccination history including COVID-19 and other routine vaccinations including influenza or pneumococcal.

Baseline samples will be taken as soon as possible after consent and enrolment into the study. The remote cohort will receive a DBS testing kit in the post and the in-person cohort will provide blood, saliva and nasal samples (described below) during a clinic visit.

Visit 2: This visit is to capture samples just before administration of the booster vaccine.

The purpose of this visit is to measure the lowest antibody level just before vaccination. Ideally this will be within the week prior to the booster vaccination although, patients can be recruited at any point during their vaccine journey (pre or post vaccine).

This visit may be shortly after the Visit 1 depending on when a participant consents. For individuals providing in-person samples the study team can omit this visit if it is less than **12 weeks after Visit 1.** The remote group will continue to complete a dried blood spot sample if they are recruited before September 2023. If recruited after this point this visit can be omitted.

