The above notification is based on most recent vaccination prior to Autumn 2023 and ticks "NO" to planning to have Autumn 2023 booster

Recruited - Study team to take bloods and other tests as per the protocol Visit 1

Visit to be arranged at 6 months from recruitment date (use date of completed registration form) Visit 4

* Please note that the blood tube requirements for Visit 1 are slightly different to other visits. Regardless of when the participant is recruited, their first attendance or first DBS is considered Visit 1. This will ensure the correct tubes are collected.

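### The primary exposure and infection window are defined by visit labels that the booster follow-up routes do not assign to people recruited after their autumn 2023 booster, and no mapping is stated

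*Protocol*

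**What the plan says.** Section 11 of the protocol names Appendix 3 as the statistical analysis plan. Its primary analysis reads: "The primary analysis will be undertaken using a logistic regression model with infection as the outcome and antibody response post-V3 as a binary variable". A later paragraph shows that V3 is a visit and not a vaccine dose: "The above analyses focus primarily on Visit 3 (4 weeks post vaccine booster". The outcome counts "all infections from ≥14 days post vaccination given between Visit 2 until Visit 4". On missing values: "Analysis will be of complete data and missing data will not be imputed".

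The visit rules elsewhere in the protocol differ from this.

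- Section 6.1 allows recruitment before or after the booster: "If patients are recruited after their booster vaccination, they will start at visit 1".
- Appendix 6 times the first sample of post-booster recruits at 28 days or more after the booster, preferably at 4-10 weeks. A closing footnote fixes the label: "Regardless of when the participant is recruited, their first attendance or first DBS is considered Visit 1".
- In the face-to-face route of Appendix 6, the next contact for these people is Visit 4, six months after the booster.
- Section 6.5.1 lets the in-person cohort skip Visit 2 if it would fall less than 12 weeks after Visit 1. For remote participants recruited after September 2023 it says: "If recruited after this point this visit can be omitted".
- The separate Visit 1 analysis in Appendix 3 adjusts for time since vaccine and has this end point: "Infection outcomes will be described up until Visit 2".

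**The concern.** Someone recruited after the autumn booster can have a sample in exactly the window that Sections 6.1 and 6.5.1 give to Visit 3, yet it carries the label Visit 1. No sample of theirs is labelled Visit 3, and their booster was not given between Visit 2 and Visit 4. Under the complete-data rule, a literal reading removes them from the primary analysis on both exposure and outcome window.

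At stake is who is in the primary analysis. If the mapping is decided once data are in hand, membership becomes a post hoc choice that depends on recruitment date. The sample size statement counts all 3000 participants as having a usable exposure.

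Two related points need the same repair. Appendix 3 describes Visit 3 as 28 days or 4 weeks after vaccination, while collection runs over 4-10 weeks. Time since vaccine is an adjustment in the Visit 1 analysis but is not listed for the Visit 3 models, where a fixed antibody cut-off is applied.

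**Working it through.** **Step 1: set the routes beside the primary definition.** The definition needs a Visit 3 sample and a vaccination between Visit 2 and Visit 4.

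| Route (Appendix 6) | Label of the post-booster sample | Visit 2 | Position of booster |
|---|---|---|---|
| In-person, recruited before booster | Visit 3 | none listed | after Visit 1 |
| Remote, recruited before booster | second DBS card, no visit number | none listed | after first card |
| In-person, recruited after booster | Visit 1, then Visit 4 | none | before Visit 1 |
| Remote, recruited after booster | first card, so Visit 1 by the footnote | none | before Visit 1 |

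Both post-booster routes fail both parts of the definition. The pre-booster routes can meet the exposure part, but the Visit 2 anchor of their infection window may not exist. No section says that a Visit 1 sample taken 4-10 weeks after the booster counts as Visit 3.

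**Step 2: see whether the Visit 1 analysis picks them up.** It is not the primary analysis, and its infections end at Visit 2, which these people do not have. It would also combine their post-booster samples with pre-booster samples. The planned adjustment for time since vaccine helps with that mixing, but the end point stays undefined.

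**Step 3: reproduce the plan's figure.** Inputs from Appendix 3: 750 low or no response, 2250 normal response, 90% power, two-sided 5%, most conservative rate 50%. With p2 the normal-response rate, p1 = p2 + d, and p̄ the weighted mean rate,

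power = Φ{ [d − 1.96·√(p̄(1−p̄)(1/n1+1/n2))] / √(p1(1−p1)/n1 + p2(1−p2)/n2) }.

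At p2 = 0.50 and d = 0.0681, p1 = 0.5681 and p̄ = 0.5170. The two standard errors are 0.0211 and 0.0209, so the argument is (0.0681 − 0.0413)/0.0209 ≈ 1.28, which gives 90% power. The odds ratio is (0.5681/0.4319)/1 = 1.315, and ln(1.315)·√3/π = 0.151. This matches the lower end (0.15) of the stated standardised effects for infection. The upper end, 0.36, corresponds to a normal-group rate of about 3-4%, which the protocol does not state, so only the lower end is reproduced directly.

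**Step 4: illustrate a loss.** The protocol does not give the share recruited after the booster, so the shares below are assumptions. The 1:3 split is kept.

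| Assumed share lost | N | Detectable difference at 50% (points) | Power for 6.8 points at 50% |
|---|---|---|---|
| 0% | 3000 | 6.8 | 90% |
| 10% | 2700 | 7.2 | 87% |
| 20% | 2400 | 7.6 | 83% |
| 40% | 1800 | 8.8 | 71% |
| 50% | 1500 | 9.6 | 63% |
| 60% | 1200 | 10.7 | 53% |

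At a 20% infection rate the detectable difference is 5.7 points with nobody lost, 6.4 with 20% lost and 7.4 with 40% lost.

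**The case against.** The best reply is that nobody is excluded by name. Sections 6.1 and 6.5.1 and Appendix 2 describe Visit 3 by time since vaccine, so an analyst could reasonably treat a post-booster recruit's first sample as the Visit 3 measurement. The footnote in Appendix 6 says the Visit 1 label is there so that the right blood tubes are used. Appendix 6 instructs sites, may change again, and defines no analysis set. The explicit step from Visit 1 to Visit 4 appears only in the face-to-face route, planned for 400 of 3000; for the remote cohort the Visit 1 label rests on the footnote alone.

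Most of this stands, and it limits the point to an unstated mapping. Four stronger readings are tempting, and the documents do not support them.

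- *That the plan drops these participants.* That follows only from a literal reading of the labels, and the purpose of the label suggests it was not meant.
- *That every such first sample is a valid Visit 3 measurement.* Appendix 6 sets only a 28-day minimum and treats 4-10 weeks as preferred, so some samples will be later.
- *That the study becomes underpowered.* At an assumed 40% loss the detectable difference is still under the stated 10%. At a 50% rate that limit is passed only somewhere between 50% and 60% loss. Appendix 3 also promises monthly review of the sample size assumptions.
- *That the odds ratio is biased.* Selection by recruitment date is possible, but no direction or size can be derived. The protocol also gives no waning rate, so misclassification across 4-10 weeks cannot be sized, and a sensitivity analysis with antibody as a continuous variable is already planned.

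The reply does not remove the conflict. Appendix 3 and Appendix 6 belong to the same protocol version and define the same measurement differently. This is a contradiction in the text, not a detail left for a later document.

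**Conclusion.** The point holds as a conflict of definitions affecting the primary analysis population. Appendix 3 anchors exposure and infection window to Visits 3 and 2. Section 6.1, Section 6.5.1 and Appendix 6 create participants who have neither visit and whose booster precedes their first visit, and they leave Visit 2 missing for many others. Applied as written with complete data only, the rule would lose post-booster recruits who have a sample in the 4-10 week window.

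The size is unknown because the affected share is not stated. The group is expected, since this version is dated 26.11.2023, with autumn boosters under way, and gives it its own route. The power figures are illustrations under assumed shares and a constant 1:3 split. The main harm is an ambiguous primary population; lost precision comes second. The differing descriptions of Visit 3 timing and the covariate missing from its models are smaller and can be settled in the same edit.

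**What to change.** In Appendix 3:

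1. Define the primary exposure as the first sample taken 4-10 weeks after the index vaccine, whatever its visit label. Put later samples in a sensitivity analysis.
2. Anchor the infection window to the index vaccine date instead of Visit 2. For people recruited after the booster, count infections only from their qualifying sample, because part of their risk period has passed before they enter.
3. In the Visit 1 analysis, use a Visit 1 sample only when it precedes the index vaccine, and end at the booster date when there is no Visit 2.
4. Add weeks from vaccine to sample as a covariate in the Visit 3 models, as the Visit 1 analysis already does.
5. Replace the 28-day and 4-week descriptions of Visit 3 with the 4-10 week window, and add a line to Appendix 6 stating how its samples map to the analysis.

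The cost is revised wording, one derived variable from vaccination and sample dates, and a small sensitivity analysis. Post-booster recruits will have shorter counted follow-up, so follow-up time should be reported by recruitment route. The change should be made before the antibody and infection data are analysed together.
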